## Project Protocol

### Experimental design

The study consists of a mechanistic randomized placebo-controlled clinical trial with a mixed experimental design, whose objective is to assess which variables that have been linked to central sensitization (CS) in chronic pain patients can predict the response of chronic low back pain (CLBP) patients to spinal manipulative therapy (SMT). In order to do this, clinical, psychophysical and inflammatory variables will be measured in CLBP patients, which will be exposed to either SMT or a placebo SMT for 12 visits over a 4-week period. Another group made up of healthy volunteers will be used to determine the reference values of the same variables in a healthy population and compare them with the clinical population, before and after exposure. The primary outcome measures and main clinical variables are pain intensity and disability. All variables will be measured before the first SMT session, as well as at the end of the twelfth and last session, except for pain intensity, which will be measured at the start of each session for exploratory reasons.

**Figure 1.** Study protocol for the clinical trial

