#### *Adverse events reporting*

At the beginning of any of the follow-up SMT or placebo sessions, each patient will complete an online questionnaire without the presence of the investigator, answering whether they have suffered any adverse effects that they feel could be related to the treatment received. A clinical trial identified the following adverse effects as those most commonly reported after chiropractic treatment based on lumbar SMT: muscle stiffness, increased pain, radiating discomfort, and others (Walker et al., 2013). Following the example of this study, adverse effects will be classified into these categories, in addition to indicating whether they were triggered immediately, up to 24 hours, or more than 24 hours after the previous session, whether their duration was of minutes, hours (< 24 hours), between 24 and 48 hours, or longer than 48 hours (Walker, et al., 2013), and according to their intensity (very mild, mild, moderate, severe, very severe). A 3-point increase in the NRS-11 or the reporting of moderate to severe adverse events in three consecutive visits will raise the alert and the patient will be interviewed to determine whether care should be interrupted.

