Official Title:

Efficacy of Chiropractic Spinal Manipulative Therapy in Patients With
Primary Chronic Low Back Pain: a Mechanistic Randomized Controlled
Trial

NCT number: Not Available

Unique Protocol ID: SMTCLBP

Date: December 15th, 2021

Statistical analyses

The normal distribution of the data will be verified using the Kolmogorov-Smirnov test. Data deviating from normality will be transformed to obtain a normal distribution before being entered into the data analysis. The two main outcome variables (clinical pain intensity and disability related to low back pain) will be compared between groups (SMT vs. placebo) over time (baseline and session 12) using a mixed analysis of variance. Average pain intensity since the previous treatment visit and in the seven days prior to the initial visit will be the variable used for statistical analyses. With an exploratory objective, the secondary variables (PCS, CSI, BDI-II, GAD scores, PPTs, degree of pain widespreadness, urinary cytokine levels, number and severity of reported adverse effects, presence of leg pain, pain medication use) will be compared between groups (SMT vs placebo) over time (baseline and session 12) using another mixed analysis of variance. To test a priori hypotheses, significant effects will be decomposed using planned comparisons. For the rest of the effects, Tukey's HSD will be used for testing any pair-wise comparisons between group means.

Pearson's product-moment correlation analyses will be carried out to examine the association between primary variables and secondary variables that demonstrate significant effects between groups over time. Subsequently, two multiple regression models will be used to examine the predictors of improvement in clinical pain and disability over time in patients who have received SMT, using secondary variables with a significant association with the primary variables. The secondary variables used for this analysis will be: baseline PCS and CSI score, baseline PPTs in the primary pain region, baseline TNF- α levels, and baseline expectations of pain relief. In addition, in another

regression model, the changes (delta) in these variables (except expectations of pain relief, since it is only measured at baseline) throughout the 4 weeks of treatment will be used as predictor variables. This is done to identify the variables most associated with clinical evolution, in order to answer the mechanistic question.

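### The SAP tests adverse effects with a baseline-versus-session-12 model, but they are reported only from session 2 on, so no baseline exists and the per-patient summaries are undefined

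*SAP*

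**What the plan says.** The SAP (Statistical analyses) names a set of exploratory secondary variables that includes "number and severity of reported adverse effects, presence of leg pain, pain medication use". All of them are to be compared between SMT and placebo "over time (baseline and session 12) using another mixed analysis of variance".

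The protocol (Adverse events reporting) sets the collection schedule: "At the beginning of any of the follow-up SMT or placebo sessions, each patient will complete an online questionnaire". The question asked is whether the patient has had "any adverse effects that they feel could be related to the treatment received". Onset is timed from the previous session, and each effect is graded on five levels from very mild to very severe.

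The protocol (Experimental design) also has a general sentence: "All variables will be measured before the first SMT session, as well as at the end of the twelfth and last session", with pain intensity as the only stated exception.

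Neither document says how a patient's reports become one number or one severity value.

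**The concern.** A two-time-point mixed ANOVA needs a value at both times. An effect attributed to treatment cannot be reported before any treatment, so the planned model lacks one of its two columns. The analyst would have to decide three things that the SAP leaves open: what to enter at baseline, whether session 12 means that visit's report or everything reported up to it, and how to reduce several ordinal grades to one.

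This is the only between-arm comparison of adverse effects in the SAP, so these decisions would be made with the data in hand. They also carry one step further. The SAP takes secondary variables with a significant between-group effect over time into correlations with the primary outcomes, so the reading chosen can decide whether adverse effects enter that step.

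**Working it through.** **The plan's own figure.** The documents give no adverse-effect rate, power or sample size. The only figure tied to this type of model is the 34 per group (68 in total) for the primary outcomes. With f = 0.175, correlation 0.5 and alpha 0.05, the group-by-time test has noncentrality f² × N × 2/(1 − 0.5). Power is 0.7997 at N = 66 and 0.8116 at N = 68. The stated figure reproduces and is not in question.

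**Number of reports.** There are 12 sessions (protocol, Independent variables). Reports are taken at follow-up sessions only, so at sessions 2 to 12, which is 11 reports. The session-12 report alone is 1/11 = 9% of them.

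**The model with a zero baseline.** Let y be the post-treatment value and 0 the baseline.
- The interaction test is a two-sample t-test on y − 0 = y.
- The group test is a two-sample t-test on (y + 0)/2 = y/2. Rescaling does not change t, so the two F values are equal. In one simulated data set with 50 per arm, both were 3.66, as was the squared t on y.
- The time test asks only whether the mean of y differs from zero, that is, whether any effects occurred (F = 40.7 in the same data set).

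If baseline is left missing instead, the model cannot be fitted.

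**Power under the two readings of session 12.** Inputs: 50 per arm (protocol, Sample size calculation). Assumptions: per-session risks of 10% (SMT) and 5% (placebo), at most one event per report, and within-patient correlation ρ of 0, 0.1 or 0.3. The same two-sided t-test is used throughout (98 degrees of freedom, critical value 1.984).

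- Session-12 report only: difference 0.05; standard error √[(0.10×0.90 + 0.05×0.95)/50] = √(0.1375/50) = 0.0524; ratio 0.95. Exact enumeration gives power of 14%.
- Cumulative count over 11 reports: difference 11 × 0.05 = 0.55; summed variance 11 × 0.1375 × (1 + 10ρ) = 1.5125 × (1 + 10ρ); standard error √[1.5125 × (1 + 10ρ)/50].

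| ρ | Difference / standard error | Simulated power, cumulative count |
|---|---|---|
| 0 | 3.16 | 88% |
| 0.1 | 2.24 | 61% |
| 0.3 | 1.58 | 36% |

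At 20% against 10%, the session-12 report has 28% power and the cumulative count more than 99%, 91% and about 65%. At 50% against 25%, the figures are 75% and 100%, 100% and 99%.

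Under equal risks of 5%, 10% and 25%, the type I error of the cumulative t-test was 4.6 to 5.1%. That reading is therefore a sound comparison of arms.

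**Severity.** Under the same assumptions at 10% against 5%, the share of patients with no effect in 11 reports at ρ = 0 is 0.90¹¹ = 31% (SMT) and 0.95¹¹ = 57% (placebo). At ρ = 0.3 the shares are 63% and 80%. How these patients are coded would dominate any severity comparison.

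**The case against.** The analysis is labelled exploratory. The most natural meaning of number of reported effects is the total reported, and with a zero baseline the interaction then compares those totals correctly. This stands: the cumulative reading loses no power, with 88%, 61% and 36% against 88%, 60% and 34% for a rate ratio at 10% against 5%. What remains against it is that the SAP does not say this is meant, and that it plans no rate ratio with an interval.

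Three stronger readings are tempting, and the documents do not support them.

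- A reader might infer that power ranges from 6% to 89% depending on the reading. The 6% comes from Fisher's exact test on the session-12 report, which the SAP does not plan. With the same t-test the low end is 14%, and the high end requires independent reports within a patient.
- A reader might infer that patients without an effect have no severity value and would be dropped, so that the arms compared are no longer the randomized groups. The questionnaire first asks whether any effect occurred, so a negative answer is recorded and maps to none. Nothing in the SAP says such patients are left out.
- A reader might take the general sentence in Experimental design as supplying a baseline. It cannot do so for effects defined by treatment received and timed from the previous session.

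The review of individual patients, where "the patient will be interviewed to determine whether care should be interrupted", is a separate process and does not use this analysis. Leg pain and medication use in the same list are a separate minor point.

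**Conclusion.** The concern holds as a specification error: the stated model does not fit the data the protocol collects. That there is no baseline follows from the text alone and needs no assumption. The same is true of the missing rules for session 12 and for severity.

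The size of the consequence depends on assumed risks. At 10% against 5% per session, reading session 12 as a single report would leave about 14% power, where the cumulative count has 36 to 88%. If the cumulative count is what was meant, no power is lost and the defect is one of definition and reporting. The calculation allows one event per report, although a report could contain several.

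The harm is limited. Every report is collected in any case, the comparison is exploratory, and the primary outcomes, sample size and individual safety monitoring are unaffected. It should be corrected because correction is cheap and removes a free choice on safety data.

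**What to change.** Take adverse effects out of the pre/post ANOVA and compare SMT with placebo once, over all reports from sessions 2 to 12, labelled exploratory.

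- **Number:** events per completed report, as a rate ratio with 95% CI from a count model that allows for overdispersion (quasi-Poisson or negative binomial), with the log of reports completed as offset. Sessions attended would be the wrong offset, because the first session yields no report. Patients with no completed report are counted and described separately. At 10% against 5%, the interval would run from the estimate divided by, to the estimate multiplied by, about 1.57, 1.88 or 2.45 at correlation 0, 0.1 or 0.3.
- **Severity:** worst intensity per patient on six ordered levels (none plus the protocol's five), by a rank test. Patients who report no effect are coded none, not left out.
- **Limit to state:** effects after a patient's last attended session, including after session 12, are not captured by the Adverse events reporting schedule.

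The cost is SAP wording and a few lines of analysis. No new data are needed and no trial procedure changes.

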## **Procedures**

The study will have a total estimated duration of one year, during which each patient will participate in 12 sessions divided into 3 weekly sessions for 4 weeks (see Figure 1). Once this phase of the study has been completed, patients who had been assigned to the placebo group will be offered the possibility of receiving the equivalent

“real” treatment at the MCC free of charge. Patients who received SMT may continue at their own cost. In addition, 4 weeks after the end of the study, patients will be contacted to request that they provide data on their pain intensity and disability, as described above, as well as responses to the questionnaires proposed as follow-up. Healthy volunteers will participate in two visits, baseline and follow-up after 4 weeks.

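### The SAP analyses adverse effects by a baseline-to-session-12 mixed ANOVA although baseline can only be zero, and it plans no comparison by arm of patients affected, by type or by worst intensity

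*SAP*

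**What the plan says.** The SAP, under Statistical analyses, puts adverse effects in a list of secondary variables with an exploratory purpose. The list ends with "number and severity of reported adverse effects, presence of leg pain, pain medication use) will be compared between groups (SMT vs placebo) over time", the times being "baseline and session 12) using another mixed analysis of variance". The three-group analyses at the end of the SAP do not include adverse effects, so this is the only comparison of them in either document.

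The protocol, under Adverse events reporting, says when and what is collected. The online form is completed "At the beginning of any of the follow-up SMT or placebo sessions", and it asks "whether they have suffered any adverse effects that they feel could be related to the treatment received". Effects are then classified by type (stiffness, more pain, radiating discomfort, other), by onset, by duration, and "according to their intensity (very mild, mild, moderate, severe, very severe". A 3-point rise in the pain rating, or moderate to severe effects at three consecutive visits, "will raise the alert and the patient will be interviewed to determine whether care should be interrupted".

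Under Procedures, the later contact is described thus: "4 weeks after the end of the study, patients will be contacted to request that they provide data on their pain intensity and disability". The questionnaires are requested as well. Adverse effects are not named there.

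**The concern.** The analysis rule does not fit the data it is applied to. Before session 1 no treatment has been received, so a treatment-related effect has no baseline value other than zero by definition. The Experimental design section says in general terms that variables are measured before the first session. That does not supply one, because the adverse-effect question is tied to treatment already given.

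The SAP also leaves open whether the session-12 value is that day's form or the total over the course. Nor does it say how severity is scored for a patient with no effect or with several.

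At stake is the safety report of a randomized trial of 12 manipulation sessions. Readers will want to know how many patients in each arm had an effect, of what kind and how bad at worst. The protocol collects what is needed, but the plan specifies no such comparison.

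**Working it through.** **Inputs.** 50 patients per arm (Protocol, Sample size calculation); 12 sessions (Protocol, Independent variables); forms at sessions 2 to 12, so 12 − 1 = 11 forms, covering effects after sessions 1 to 11. Neither document gives an adverse-effect rate, so all counts below are assumptions. The plan has no figure of its own to reproduce on this point: its 34 per group is for pain and disability.

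**1. What the ANOVA becomes with a zero baseline.** Let y be a patient's session-12 value, with baseline 0. The patient's mean over the two times is y/2 and the change is y. The group effect compares mean y/2 between arms and the group-by-time interaction compares mean y. Both are multiples of the same variable, so both F values equal the squared two-sample t on y.

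Example with course totals:
- SMT: 10 patients with 2 effects and 10 with 1 (30 effects, mean 0.60, variance 0.653).
- Placebo: 1 patient with 2 and 8 with 1 (10 effects, mean 0.20, variance 0.204).
- Pooled variance (0.653 + 0.204)/2 = 0.4286.
- t² = (0.60 − 0.20)² / (0.4286 × 2/50) = 0.16/0.01714 = 9.33 on 98 df, p = 0.003. Group F and interaction F are both 9.33.
- Time F = 0.40² / (0.4286/100) = 37.3. It says only that some effects occurred, since nobody can start above zero.

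**2. Reading session 12 as that day's form.** 1 of 11 forms is used (9% of reports at a constant rate) and 10 are not. With an assumed independent risk per interval of 2%, 5% or 10%, the chance of at least one effect over 11 intervals is 1 − (1 − p)¹¹ = 20%, 43% or 69%, against 2%, 5% or 10% on a single form.

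**3. Reading session 12 as the course total.** Take 20 effects in each arm: 20 SMT patients with 1 each, 10 placebo patients with 2 each.
- Raw counts: mean 20/50 = 0.40 in both arms, so F = 0.
- The SAP transforms non-normal data but names no transformation; two common ones are assumed. Both leave zero at zero, so step 1 still applies.
- log(1+x): means 0.277 and 0.220, pooled variance 0.1574; F = 0.0575² / (0.1574 × 0.04) = 0.53.
- Square root: means 0.400 and 0.283, pooled variance 0.2857; F = 0.1172² / (0.2857 × 0.04) = 1.20.
- Neither is significant at 5%.
- Patients affected: 40% versus 20%. Wilson limits are 27.6% to 53.8% and 11.2% to 33.0%. The Newcombe lower limit is 0.20 − √(0.124² + 0.130²) = 0.020 and the upper is 0.20 + √(0.138² + 0.088²) = 0.364. The difference is 20 points, 95% CI 2.0 to 36.4.

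**4. Severity.** The scale starts at very mild and has no grade for no effect. Score it 1 to 5, with 10 SMT patients averaging 2 and 5 placebo patients averaging 3. Coding no effect as 0 gives 20/50 = 0.40 versus 15/50 = 0.30. Leaving it missing gives 2.0 versus 3.0. The direction depends on a rule that is not stated.

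**The case against.** **The between-arm test survives.** On the course-total reading, step 1 shows a valid two-sample comparison with an uninformative time term added. This stands: the zero baseline does not bias the comparison of arms.

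**The course total is the more natural reading.** Effects are collected at every follow-up session and the SAP speaks of the number reported. This is fair. A reader might infer that the plan discards ten-elevenths of the reports; the documents do not settle that, and the loss applies only if session 12 means that day's form.

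**The SAP transforms non-normal data.** A reader might infer from the raw-count example that the planned analysis cannot see a difference in patients affected when totals are equal. That goes too far. If 20 effects fall on 20 versus 4 patients, F is 0 on raw counts but 2.50 (p = 0.12) after log(1+x) and 3.94 (p = 0.0499) after a square root. What remains is that a transformed count is still not a number of patients, and the choice of transformation is open.

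**A descriptive table is likely anyway.** The protocol classifies effects by type and intensity, and a negative answer to the form's opening question is a natural zero for severity. Both points are reasonable, but no table by arm is stated, and neither is a rule for combining several effects in one patient.

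**Patient safety does not rest on this ANOVA.** Correct: the alert and interview deal with individual patients during the course.

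**Conclusion.** The point holds, at modest size. The planned time factor is meaningless for treatment-related effects. The session-12 value and the severity score are undefined, and no comparison of patients affected by arm is specified. The consequence is limited to exploratory safety reporting. A reader might infer that the trial's main result is in doubt or that harms are not monitored; neither follows, since pain and disability are analysed separately and the alert rule is in place.

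That baseline is zero and that ANOVA reduces to a t test follow from the documents and algebra alone. The F values, percentages and intervals rest on invented counts at 50 per arm with every patient analysed. The F values after transformation also rest on two transformations that the SAP does not name.

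**What to change.** In the SAP, take number and severity of adverse effects out of the two-time ANOVA. Add one table by arm, cumulated over all follow-up reports, in patients who received at least one session, with those who returned no form shown separately:

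- number and percent with at least one effect: overall, by the protocol's four categories, and by worst intensity;
- risk difference with 95% CI for each (Newcombe intervals suit these numbers);
- total number of effects, because counting patients gives one effect the same weight as several;
- numbers meeting the alert and numbers whose care was interrupted.

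State that the table covers effects after sessions 1 to 11. Optionally, send the same form once more 2 to 3 days after session 12, before any further treatment. The 4-week contact is too late for this, because "patients who had been assigned to the placebo group will be offered the possibility of receiving the equivalent" real treatment once their course ends.

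The cost is SAP wording and one table from data already collected, with no change in sample size; the optional form is one more online questionnaire per patient. The price is imprecision. At 50 per arm, 10 versus 5 patients affected gives 10 points (95% CI −4.3 to 24.2). With 5 placebo patients affected, the interval excludes zero only from 13 SMT patients upward (16 points, 0.8 to 30.7). If 0 of 50 meet the alert, the exact upper 95% limit is 1 − 0.025^(1/50) = 7.1%. The table should therefore be presented as estimates rather than tests.

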### Patient sample

For this study, participants will be recruited through the network of contacts of MCC and the Chiropractic Research Network. To be included in the study, patient participants must be of legal age (18-70 years old), receive a diagnosis of primary CLBP of at least 3-month duration, with or without leg pain (according to a clinical examination carried out at the Madrid College of Chiropractic – MCC). If pain affecting the low back or lower limb is suspected to be predominantly of neuropathic origin, the patient will be excluded (Kosek et al., 2021). Additionally, patients will be excluded from the study if they present any of the following criteria: evidence of specific pathology as the cause of their CLBP, diagnosis of mental illness or pain of equal or higher intensity affecting the hand / thumb or regions near the lumbar spine, use of corticosteroids, opiates or anti-cytokine medication, pregnancy, lumbar fusion surgery or recent laminectomy, having received SMT in the 12 months prior to the beginning of the study (Gerhardt et al., 2017; Klyne et al., 2019; Smart et al., 2012). The only exception to this will be patients with a diagnosis of anxiety and depression, as these conditions are very frequently comorbid with CLBP (Gore et al., 2012; Wong et al., 2021) and may also suggest a CS phenotype (Aoyagi et al., 2019; Smart, et al., 2012). Candidates interested in participating in the study will initially complete a questionnaire with the selection criteria, either in person at the MCC or online. If the criteria are met, patients will be scheduled an appointment where they will be provided with an information sheet so that they can read all the information in detail and ask any questions they see fit, before signing the informed consent. Subsequently, they will be referred for a clinical examination (consisting of a case history and physical examination) that will confirm the diagnosis of primary CLBP (see Figure 1–0).

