### *Clinical examination variables*

During the case history taken, data on the characteristics of the patients' CLBP will be collected. Pain intensity will be the main primary outcome. Patients will evaluate the intensity of their CLBP at the current time, as well as the mean, minimum and

maximum pain throughout the preceding seven days or since the time of the previous session, once the study is underway, according to the brief pain inventory (de Andres Ares et al., 2015; Tan et al., 2004). Pain intensity will be collected via an online questionnaire without the presence of any investigator in every visit for descriptive reasons, although only the baseline and the final values will be used for statistical analyses. The other primary outcome will be the degree of disability provoked by CLBP. Upon completing the case history, patients will fill out the Oswestry low back disability index questionnaire (Alcántara-Bumbiedro et al., 2006), which will also be completed at the end of the study.

Additionally, other pain variables will be recorded at baseline for exploratory purposes: CLBP trajectory (duration and frequency) and localization. For the later, patients will draw the area affected by their pain on a tablet, using an application (Symptom Mapper) that will allow the degree of widespreadness of their pain to be calculated (Ellingsen et al., 2021). They may also indicate any pain present of less intensity outside the low back region, as any symptom of higher intensity will necessarily exclude the patient from the study. Additionally, clinicians will determine whether the CLBP is proportionate or disproportionate to the degree or nature of the injury or pathology, with a discrete or rather diffuse distribution, according to criteria that have been defined in the literature (Nijs et al., 2015; Smart, et al., 2012). A diffuse rather than a discrete distribution has been identified as a key criterion suggesting a CS phenotype (Kosek, et al., 2021; Smart, et al., 2012).

Finally, other variables will be reported such as the intake of pain medication compatible with the selection criteria, both at baseline and at the end of treatment. Similarly, whether the patient regularly smokes will be reported at baseline, since smoking has been associated with increased serum levels of pro-inflammatory cytokines.

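### The SAP's transform-to-normality rule cannot be met by yes/no secondary variables, and the change-based mixed ANOVA is a weak test for them; the coding of medication use is also not stated

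*SAP*

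**What the plan says.** The SAP (Statistical analyses) opens with a general rule: "The normal distribution of the data will be verified using the Kolmogorov-Smirnov test", followed by "Data deviating from normality will be transformed to obtain a normal distribution before being entered into the data analysis". No variable is exempted, and nothing is said about what happens if a transformation fails.

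The secondary comparisons are introduced by "With an exploratory objective, the secondary variables". The list of variables ends with "presence of leg pain, pain medication use) will be compared between groups (SMT vs placebo) over time (baseline and session 12", and the method is "over time (baseline and session 12) using another mixed analysis of variance". The SAP names no method for categorical data.

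On scale and timing, the Protocol gives the following:

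- **Leg pain.** Patients are eligible "with or without leg pain" (Patient sample). Under Clinical examination variables, "other pain variables will be recorded at baseline for exploratory purposes: CLBP trajectory (duration and frequency) and localization"; no session-12 leg-pain assessment is described there. Experimental design, however, says that all variables are measured before the first session and at the end of the twelfth.
- **Medication.** The Protocol records "the intake of pain medication compatible with the selection criteria, both at baseline and at the end of treatment" (Clinical examination variables). It does not say whether this is yes/no, a count, a frequency or an amount.

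**The concern.** A rule that must be applied but cannot be leaves the analyst to improvise once the data are in hand. That is the position for leg pain, and for medication use if it is recorded as yes/no.

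Medication use is the variable with practical weight. It shows whether an arm difference in pain is accompanied by a difference in analgesic intake, which bears on how the pain result is read. The useful quantity is the difference in use at session 12, allowing for baseline, with a confidence interval. The SAP also carries secondary variables with significant group-by-time effects forward to correlation with the primary variables, so the choice of test affects what is examined next.

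**Working it through.** **Inputs.** From the Protocol (Sample size calculation): 50 patients per arm. From the SAP: two occasions, baseline and session 12. The documents give no rates of leg pain or medication use, so every prevalence and correlation below is an assumption.

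**The plan's own figure for this method.** The only figure tied to the group × time ANOVA is the sample size for the primary outcomes. With f = 0.175, two measures, correlation 0.5 and N = 68, the noncentrality is f² × N × 2/(1 − 0.5) = 0.030625 × 68 × 4 = 8.33. Power is 0.812 at N = 68 and 0.7997 at N = 66. The stated 68 (34 per group) is reproduced. It does not depend on leg pain or medication use.

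**Step 1: would the normality rule be triggered?** For a 0/1 variable with prevalence p ≤ 0.5, the Kolmogorov-Smirnov distance from a normal with the same mean and SD is D = (1 − p) − Φ(−√(p/(1 − p))). It is symmetric for p above 0.5.

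- p = 0.5: 0.5 − Φ(−1) = 0.341
- p = 0.3: 0.7 − Φ(−0.655) = 0.444
- p = 0.2: 0.8 − Φ(−0.5) = 0.491
- p = 0.1: 0.9 − Φ(−0.333) = 0.531

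With mean and SD estimated from the data, the 5% critical value is about 0.886/√n: 0.125 at n = 50 and 0.089 at n = 100. Every D above exceeds these by a wide margin, so normality is rejected.

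**Step 2: can the transformation succeed?** A function of a two-valued variable takes at most two values. If those values differ, the result is a linear rescaling of the original and D is unchanged. Log, square-root, exponential, arcsine and power transformations were tried on 0/1 data; each returned two values perfectly correlated with the original. The required step cannot be completed.

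**Step 3: does the ANOVA fail on 0/1 data?** With two occasions, the interaction F is the square of a two-sample t on change scores. In simulation at 50 per arm with no arm difference, its type I error was 0.037 to 0.051 (prevalences 0.05 to 0.5, latent correlations 0.5 to 0.9), slightly conservative when use is rare. The test is usable under the null.

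**Step 4: what does testing change cost?** Assume 50% use in both arms at baseline, 50% v 30% at session 12, and a latent normal correlation of 0.5.

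- Arm at 50%: probability of use on both occasions 1/3; covariance 1/3 − 0.25 = 0.083; variance of change 0.25 + 0.25 − 2 × 0.083 = 0.333.
- Arm at 30%: probability of use on both occasions 0.2216; covariance 0.2216 − 0.15 = 0.0716; variance of change 0.25 + 0.21 − 2 × 0.0716 = 0.317.
- Standard error of the difference in change: √((0.333 + 0.317)/50) = 0.114. Noncentrality 0.20/0.114 = 1.75 on 98 df gives power of about 0.41.
- Logistic model of session-12 use on arm with baseline use as covariate, same scenario, by simulation: power of about 0.58.

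The loss arises because the correlation on the 0/1 scale is only about 0.083/0.25 = 0.33. At that level, subtracting the whole baseline value adds more noise than it removes.

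**The case against.** The best defence is that the ANOVA on 0/1 data is a linear-probability analysis that holds its size, and that its cell means are proportions. The interaction contrast is then the arm difference in change in proportions, which is interpretable, and the SAP provides for planned comparisons. The comparisons are also labelled exploratory. All of this stands, and it limits the point.

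Three stronger readings are tempting, and the documents do not support them:

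- **A reader might infer that medication use is a yes/no variable.** Neither document says so. The Protocol speaks of intake and the SAP of use, and a count, frequency or amount is equally open. What can be said is that the coding is missing and that the problem applies if it is yes/no.
- **A reader might infer that the whole analysis is impossible, or that the F test is invalid.** Only the normalising step is impossible.
- **A reader might infer that the dependence of binomial variance on prevalence breaks the test.** If use went from 10% to 40%, the variance would go from 0.1 × 0.9 = 0.09 to 0.4 × 0.6 = 0.24. That is a difference between occasions, and the change-score test does not assume equal variance across occasions. Simulating 10% to 40% in both arms at 50 per arm, with latent correlations 0, 0.5 and 0.8, gave type I error of 0.053, 0.049 and 0.051.

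Nor can it be concluded that leg pain is certainly not measured at session 12. Experimental design implies that it is, while Clinical examination variables describes localization at baseline only.

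**Conclusion.** The point holds in a limited form. For leg pain, and for medication use if it is yes/no, the SAP prescribes a step that cannot be carried out and offers no alternative. The mixed ANOVA that follows is computable and keeps its type I error near nominal, but it is an inefficient choice for these variables: power of about 0.41 against 0.58 in one assumed scenario (50 per arm, 50% baseline use, 50% v 30% at session 12, latent correlation 0.5). The failure of the transformation needs no assumption beyond a two-valued variable. The power loss depends on the assumed rates and correlation and would shrink as the correlation between occasions rises.

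The consequence is confined to exploratory comparisons and the correlations selected from them. The primary analyses, the five named regression predictors and the sample size do not use these variables. This is a minor but worthwhile correction.

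**What to change.** Amend the SAP before the allocation is unblinded:

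1. Exempt yes/no variables from the normality check and transformation rule, and remove them from the mixed-ANOVA list.
2. State how medication use is coded.
3. If it is yes/no, fit a logistic model of session-12 use on arm with baseline use as covariate. From it, report the standardised (marginal) arm difference in proportions with a 95% CI: average each patient's predicted probability under each arm in turn, and take the difference.
4. If it is an amount or frequency, keep that scale and use a baseline-adjusted model suited to it. Reducing it to yes/no would discard information.
5. Reconcile the Protocol's Experimental design and Clinical examination variables sections on whether leg pain is reassessed at session 12. If it is, analyse it as in item 3; if not, describe it at baseline only and drop the comparison over time.

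The cost is one more model and a sentence or two in the SAP. Medication intake is already planned at both time points, so it needs no new data.
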